5.5 Pharmacokinetic, Pharmacodynamic, Pharmacogenomic, and Other Biomarker Analyses

5.5.1 Pharmacokinetic Analyses

Plasma concentration of lenvatinib versus time data will be listed. Pharmacokinetic data will be summarized using n, mean, SD, median, Q1, Q2, minimum, and maximum.

Plasma concentration of lenvatinib versus time data from all cohorts will be pooled and analyzed using a population PK approach to estimate population PK parameters. The analysis will be detailed in a separate analysis plan.

5.5.2 Pharmacodynamic, Pharmacogenomic, and Other Biomarker Analyses

Correlation between clinical response to lenvatinib treatment or AEs associated with lenvatinib treatment and blood or tumor biomarkers may be examined using descriptive statistics and graphic displays as appropriate. A separate analysis plan will be developed for the analyses of PK/pharmacodynamics, pharmacogenomic and other biomarker analyses. Results from these analyses will not be included in the clinical study report but reported separately.

5.6 Safety Analyses

All safety analyses will be performed on the Safety Analysis Set. Safety data, including treatment-emergent adverse events (TEAEs), clinical laboratory parameters, vital signs, 12-lead ECG results, and left ventricular ejection fraction (LVEF) will be presented by study cohort and summarized on an “as treated” basis using descriptive statistics (e.g., n, mean, SD, median, Q1, Q3, minimum, and maximum values for continuous variables; n (%) for categorical variables). Study Day 1 for all safety analyses is defined as the date of the first dose of study drug.

In addition, results of urine dipstick (proteinuria), occult blood in stool, KPS or Lansky play scores, and proximal tibial growth plates at scheduled time points, as well as their changes from Baseline, will be summarized by study cohort using descriptive statistics, as appropriate.

5.6.1 Extent of Exposure

5.6.1.1 Extent of Exposure of Study Drug

All parameters that represent the extent of exposure will be presented for Cohorts 1 and 3A of Phase 1, and Cohorts 2A, 2B and 3B of Phase 2. Number of cycles received will be summarized by descriptive statistics and by categories. Duration of treatment (days) for oral drug lenvatinib will be summarized by descriptive statistics. It is calculated as: Date of last dose – Date of first dose + 1. While the duration of treatment for the IV drugs, ifosfamide and etoposide (Cohorts 3A and 3B), will be counted in days as it is actually administrated.

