9.1.2 Treatment Phase

In all the cohorts, lenvatinib is administered daily (QD) and 1 treatment cycle is defined as a 28-day period for Cohorts 1, 2A, and 2B and a 21-day period for Cohorts 3A and 3B. A new treatment cycle begins every 28 days for Single-Agent Cohorts 1, 2A, and 2B or 21-day period for Combination-Treatment Cohorts 3A and 3B, irrespective of dose interruptions. See [Section 9.4.1](#) for rules regarding the calculation of lenvatinib dose based on body surface area (BSA).

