9.1.2.3 Cohort 3A: Combination Dose-Finding

Lenvatinib will be administered orally QD in combination with ifosfamide and etoposide from Day 1 to Day 3 of each cycle for a total of 5 cycles to subjects with relapsed or refractory osteosarcoma as described below and in Table 2. See [Section 9.4.3](#) for additional details on cytotoxic chemotherapy.

Table 2 Lenvatinib and Chemotherapy Doses for Combination Dose-Finding (Cohort 3A)

Dose Modification of Lenvatinib				
	Dose - Escalation	Starting Dose	De-escalation 1	De-escalation 2
Lenvatinib	RD (from Cohort 1)	20% lower than RD from Cohort 1	40% lower than RD from Cohort 1	60% lower than RD from Cohort 1

Dose Modification of Ifosfamide and Etoposide				
	No Dose Escalation	Starting Dose	De-escalation 1*	De-escalation 2*
Ifosfamide		3000 mg/m ² /day IV for 3 days	2400 mg/m ² /day IV for 3 days	1800 mg/m ² /day IV for 3 days
Etoposide		100 mg/m ² /day IV for 3 days	80 mg/m ² /day IV for 3 days	60 mg/m ² /day IV for 3 days

RD = recommended dose, *each De-escalation dose level is 20% lower than the Starting Dose.

The chemotherapy cycles will be repeated every 21 days.

Lenvatinib is administered daily as a QD dose, and ifosfamide and etoposide will be administered on Days 1 to 3 of each cycle for a total of 5 cycles. Each Chemotherapy cycle is repeated every 21 days. Six subjects with osteosarcoma (who have not received prior lenvatinib) will be enrolled first to Cohort 3A at the Starting Dose of lenvatinib (20% below the Single-Agent RD in Cohort 1) in combination with ifosfamide 3000 mg/m²/day for 3 days (ifosfamide total dose 9 g/m²) and etoposide 100 mg/m²/day for 3 days (etoposide total dose 300 mg/m²). Subjects with lenvatinib dose capped after BSA adjustment (dose must not exceed 24 mg daily) actually take lower dose level than assigned. If a subject with capped dose experiences a DLT, the DLT data from that subject will be counted to determine the RD of the combination treatment. A subject with capped dose who does not experience a DLT will be replaced for the purpose of determining the RD.

DLTs occurring during Cycle 1 will be evaluated and the next 6 subjects will be assigned a dose based on the rules for Dose Escalation and Dose De-Escalation as follows:

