9.1.2.4 Cohort 3B (Combination Expansion)

Subjects with either lenvatinib-naïve relapsed or refractory osteosarcoma or osteosarcoma subjects who progress on single-agent lenvatinib in Cohorts 1 or 2B (optional enrollment) will receive lenvatinib (at the RD identified from Cohort 3A) in combination with ifosfamide and etoposide, provided the combination of lenvatinib, ifosfamide, and etoposide in Cohort 3A (Combination Dose-Finding) is determined to be safe and tolerable.

Osteosarcoma subjects who experience progressive disease in Cohorts 1 or 2B and choose to receive the combination therapy of lenvatinib with ifosfamide and etoposide should meet only inclusion criteria numbers 6 through 17 and all the exclusion criteria except Criterion Number 6.

Subjects in Cohorts 3A and 3B will receive ifosfamide and etoposide for a maximum of 5 cycles. Subjects who discontinue ifosfamide and etoposide in Cohorts 3A and 3B (e.g., due to toxicity) prior to completing 5 cycles may continue on single-agent lenvatinib if they are benefiting from the treatment at the discretion of the investigator. Subjects who discontinue lenvatinib prior to completing 5 cycles may continue on ifosfamide and etoposide at the investigator's discretion for 5 cycles.

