9.4.1.1 Dose-Limiting Toxicity

Dose-limiting toxicity (DLT) in subjects treated with lenvatinib will be assessed according to CTCAE v4.03 ([Appendix 2](#)) and is defined as any of the following toxicities related to lenvatinib or chemotherapy drugs (ifosfamide and/or etoposide) occurring during Cycle 1 (Day 1 to Day 28) for Cohort 1, and Cycle 1 (Day 1 to Day 21) for Cohort 3A.

Hematologic Toxicity

- Grade 4 neutropenia for ≥ 7 days (≥ 10 days for Cohort 3A)
- Grade ≥ 3 thrombocytopenia with bleeding, or lasting >7 days (≥ 10 days for Cohort 3A)
- Grade ≥ 3 febrile neutropenia.(lasting ≥ 7 days for Cohort 3A)
- Next course of chemotherapy delayed for ≥ 7 days (Cohort 3A)

Non-Hematologic Toxicity

- Grade ≥ 3 nonhematological toxicity persisting more than 7 days despite optimal supportive care. Isolated laboratory abnormalities that resolve within a week, allergic reactions, and symptoms related to tumor progression will be excluded.
- Grade 4 hypertension, confirmed systolic or diastolic blood pressure more than 25 mmHg above the 95th percentile for age, or an elevated diastolic blood pressure (ie, >95 th percentile for age) not controlled by a single antihypertensive medication within 14 days of use. An antihypertensive tablet or capsule that contains up to two antihypertensive ingredient medications will count as one antihypertensive medication.
- Grade 3 proteinuria
- Any recurrent Grade 2 nonhematological toxicity requiring ≥ 2 interruption and dose reductions
- Any dose interruption or reduction due to toxicity which results in administration of less than 75% of the planned dosage of lenvatinib.
- Any other Grade ≥ 3 toxicity (hematologic and nonhematologic) assessed as related to lenvatinib treatment, and which in the opinion of the principal investigator and Eisai medical monitor constitutes a dose-limiting toxicity

All DLTs must be reported to the Eisai medical monitor within 24 hours of their occurrence. Determination of a DLT will be made by the investigator and the Eisai Medical Monitor, in consultation with the PSC, as needed. Subjects who discontinue the study treatment for any reason other than DLT during Cycle 1 (Day 1 through Day 28 for Cohort 1, and Day 1 through Day 21 for Cohort 3A) will be replaced.

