Details of ifosfamide and etoposide dose interruption and reduction as well as management of toxicity can be found in the Summary of Product Characteristics (SmPC), and may be followed as per local and institutional guidelines. The SmPC will be provided to the study sites in the Investigator and Pharmacy files in the relevant local language. For additional information investigators may refer to the SmPC or Euramos-1 protocol ([ISRCTN67613327](#) [EudraCT no. 2004-000242-20](#)).

Table 4 Criteria for Dose Modification of Chemotherapy Dose

Toxicity	Grade	Action
Neutropenia	Grade 4	Monitor ANC counts every 3 days until resolved to < Grade 3
Febrile neutropenia	Grade 4	Reduce the next dose of ifosfamide and etoposide by 20%
Mucositis	Repeated grade 3 or Grade 4	Reduce etoposide by 20%
Renal Toxicity	Serum creatinine is 1.5 – 3 × ULN maximum serum creatinine for age and gender	Interrupt ifosfamide and etoposide for 1 week
Hematuria	>50 RBC/ high power field (hpf)	Interrupt ifosfamide for 1 week
Neurological Toxicity	≥ Grade 2	Interrupt and reduce ifosfamide and etoposide each by 20% of the previous dose. After 2 dose reductions subject must discontinue the chemotherapy drugs, but if benefiting, can continue on single-agent lenvatinib at the investigator's discretion

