5.6.1.2 Study Drug Administration

Total cumulative dose per subject (mg) will be summarized separately for lenvatinib, ifosfamide and etoposide by descriptive statistics. It is calculated as the sum of daily doses.

Dose intensity (mg/m²/day) will be summarized separately for lenvatinib, ifosfamide, and etoposide by descriptive statistics. It is calculated as: Total cumulative dose per subject (mg)/BSA (m²)/ Duration of treatment (day).

The percentage of received dose relative to planned dose will be summarized separately for lenvatinib, ifosfamide and etoposide by descriptive statistics. It is calculated as: dose

intensity / planned dose level $\times 100$. Interpretation: 100 means received dose was the same as the planned, 90 means that the actual dose was 90% of the planned.

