5.6.1.3 Study Drug Dose Modifications

Study drug dose modifications will be summarized separately for lenvatinib, ifosfamide, and etoposide, respectively.

Number of subjects with dose reductions, treatment interruptions, and treatment discontinuation due to AEs will be summarized by counts and percentage according to dosing data. Cycle of first dose interruption/reduction, and treatment discontinuation will be summarized by descriptive statistics. Frequency of dose interruptions will also be summarized by appropriate categories (e.g., 1, 2, 3, ≥ 4). Frequency of dose reductions will be summarized by categories (1, 2, 3).

The first dose reduction is defined as the first time the subject's daily dose level was reduced to a non-zero value from its maximum designated BSA-adjusted dose level and did not go back to the maximum designated BSA-adjusted dose level due to a reason other than BSA adjustment or dosing error. For example, 17 mg/m^2 followed by 0 mg/m^2 followed by 14 mg/m^2 . If there is only dose interruption with no reduction in dose, such an event will not be considered as a dose reduction. The second and subsequent dose reductions will be defined accordingly. In addition, time to first dose reduction among subjects with dose reduction will also be summarized.

Dose interruptions will only be determined for lenvatinib. Definition of dose interruption:

1. Only includes the scenario that before and after dose 0 mg/m^2 (interruption period), the dose levels are the same. For example: 17 mg/m^2 followed by 0 mg/m^2 and followed by 17 mg/m^2 ; 14 mg/m^2 followed by 0 mg/m^2 followed by 14 mg/m^2 .
2. If dose level reduces from previous dose level after dose interruption period (dose 0 mg/m^2), it should count as dose reduction and not dose interruption. For example: 17 mg/m^2 followed by 0 mg/m^2 followed by 14 mg/m^2 , the period with 0 mg/m^2 should not count as dose interruption instead it should count as dose reduction.
3. If after dose level 0 mg/m^2 , the subject discontinued from treatment permanently, it should count as treatment discontinuation instead of dose interruption.

Subject data listings will be provided for all dose administration records and for the variables calculated as above.

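### The SAP's received-versus-planned percentage for ifosfamide and etoposide stays at 100% when scheduled chemotherapy days are omitted or a cycle is skipped

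*SAP*

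**What the plan says.** Protocol 9.1.2.3 sets the chemotherapy schedule: "ifosfamide and etoposide will be administered on Days 1 to 3 of each cycle for a total of 5 cycles", repeated every 21 days. SAP 3.4.2 gives the Cohort 3B daily doses as ifosfamide 3000 mg/m² and etoposide 100 mg/m². Protocol 9.1.2.4 adds that subjects in Cohorts 3A and 3B "will receive ifosfamide and etoposide for a maximum of 5 cycles".

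SAP 5.6.1.1 defines duration of treatment in two ways. For lenvatinib it is the calendar span from first to last dose. For the two intravenous drugs it "will be counted in days as it is actually administrated".

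SAP 5.6.1.2 then applies one chain of formulas to all three drugs. Dose intensity is cumulative mg divided by BSA and by duration, and the percentage is dose intensity over the planned dose level, times 100. It gives one reading for all three: "Interpretation: 100 means received dose was the same as the planned", with 90 meaning 90% of plan.

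SAP 5.6.1.3 states: "Dose interruptions will only be determined for lenvatinib".

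**The concern.** For chemotherapy, the number of days given sits in both parts of the fraction. Each day given adds its dose to the cumulative total and one day to the duration; a day not given adds to neither. The percentage therefore cannot respond to missing days, although the SAP's name for it and its interpretation sentence present it as the dose received against the dose planned.

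Missed chemotherapy is foreseeable. For renal toxicity, Protocol Table 4 says "Interrupt ifosfamide and etoposide for 1 week", and other rows of that table also interrupt chemotherapy.

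This is the only planned summary that expresses delivered chemotherapy as a share of planned. A reader who takes it at its stated meaning could overstate how much of the scheduled ifosfamide and etoposide was delivered alongside lenvatinib in Cohorts 3A and 3B.

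**Working it through.** **Inputs.** Planned daily dose: 3000 mg/m² ifosfamide (SAP 3.4.2). Planned days: 3 per cycle × 5 cycles = 15 (Protocol 9.1.2.3). Planned total: 15 × 3000 = 45,000 mg/m². Duration: days given (SAP 5.6.1.1). BSA is held constant so that it cancels. Etoposide at 100 mg/m² gives the same percentages.

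**Formulas.** SAP percentage = (cumulative mg/m² ÷ days given) ÷ 3000 × 100. Share of planned dose = cumulative mg/m² ÷ 45,000 × 100.

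**The SAP's benchmark.** Full dosing: 45,000 ÷ 15 ÷ 3000 = 100%, as the SAP intends. The lenvatinib definition could not serve here. Five full, on-time cycles span 4 × 21 + 3 = 87 days, and 45,000 ÷ 87 ÷ 3000 = 17.2%. Counting days given is the only reading that returns 100% for perfect delivery.

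**Per-day reductions are captured.** A 20% cut in Cycles 2 to 5 gives 3 × 3000 + 12 × 2400 = 37,800 mg/m². The SAP percentage is 37,800 ÷ 15 ÷ 3000 = 84.0%, and the share of plan is 37,800 ÷ 45,000 = 84.0%.

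**Missing days are not captured** (illustrative; omitted days not made up):

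| Case | Days given | Cumulative mg/m² | SAP percentage | Share of planned dose |
|---|---|---|---|---|
| One day lost in one of 5 cycles | 14 | 42,000 | 42,000 ÷ 14 ÷ 3000 = 100% | 42,000 ÷ 45,000 = 93.3% |
| One of three days lost in every cycle | 10 | 30,000 | 30,000 ÷ 10 ÷ 3000 = 100% | 30,000 ÷ 45,000 = 66.7% |
| Cycle 3 skipped, Cycles 4 and 5 given | 12 | 36,000 | 36,000 ÷ 12 ÷ 3000 = 100% | 36,000 ÷ 45,000 = 80.0% |
| 20% cut throughout and one of three days lost in every cycle | 10 | 24,000 | 24,000 ÷ 10 ÷ 3000 = 80% | 24,000 ÷ 45,000 = 53.3% |

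In the last row the SAP percentage shows the reduction and misses the omission.

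**The case against.** The best defence is that the formula is sound for what it computes. The SAP uses dose level for these drugs to mean a daily mg/m², so a daily average over a daily level is a consistent comparison, and a separate duration rule for intravenous drugs is needed, as the 17.2% shows. That stands for the formula. It does not rescue the name of the quantity or the interpretation sentence, which speak of the dose received and the dose planned.

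Other planned outputs also help. SAP 5.6.1.1 presents cycles received and chemotherapy days, so days can be set against three times the cycles, if cycles are counted for chemotherapy (the SAP does not say so). SAP 5.6.1.3 summarises dose modifications separately for each drug, including reductions and discontinuations due to adverse events, and lists all dosing records. SAP 5.6.2 tabulates adverse events leading to interruption. In cohorts of 12 to 24 and about 18 lenvatinib-naïve subjects, the listings can be read directly. This limits the harm, but none of these outputs gives delivered chemotherapy as a share of planned. Table labels may also be clearer in the separate shells and programming specifications, which are not available here.

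Three stronger readings are tempting and should not be drawn:

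- *Delayed cycles are misreported.* A reader might infer this because the Cohort 3A DLT list includes "Next course of chemotherapy delayed for" 7 days or more. But if every dose is eventually given, received does equal planned and 100 is right. The summary simply carries no information on delivery over time, and the SAP does not claim that it does.
- *Lenvatinib gaps are penalised and chemotherapy delays are not.* A 7-day lenvatinib gap in 105 days means seven doses not taken (98 ÷ 105 = 93.3%). A 7-day chemotherapy delay need lose no dose, so different results are proper.
- *Early stopping is hidden.* Five cycles is a maximum, and the lenvatinib percentage likewise ignores time after the last dose.

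**Conclusion.** The point holds for scheduled days omitted within a block and for skipped cycles. In those cases the percentage stays at whatever the average administered daily dose implies, which is 100% when daily doses are unreduced, and the SAP's statement of what 100 means is wrong for ifosfamide and etoposide.

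The illustrated gaps run from 6.7 percentage points (100% against 93.3%) to 33.3 points (100% against 66.7%). They show the mechanism and are not forecasts. The documents give no frequency of omitted days or skipped cycles, and they do not say whether days lost to a one-week interruption are made up; if they are, no dose is lost. The figures also assume constant BSA, because the SAP does not say which BSA enters the formula when it changes between cycles.

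The consequence is confined to a descriptive exposure summary. Nothing in the documents carries this percentage into PFS-4, the other efficacy endpoints, the DLT assessment or the rules for the recommended dose, so it gives no ground for questioning those.

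**What to change.** For ifosfamide and etoposide only, do one of the following in SAP 5.6.1.2:

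- **(a) Relabel.** Call the quantity *average dose per administration day (% of planned daily dose)* and drop the sentence on what 100 means for these two drugs. This costs SAP wording only.
- **(b) Redefine.** Percentage = cumulative mg/m² received ÷ (assigned mg/m²/day × 3 × number of chemotherapy cycles in which at least one dose of that drug was given, maximum 5) × 100. Count cycles in which the drug was given, not study cycles started: Protocol 9.1.2 starts a new cycle after each "21-day period for Combination-Treatment Cohorts 3A and 3B, irrespective of dose interruptions". This is a small programming change using dosing records that the SAP already plans to list.

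Option (b) corrects omitted days: 14 of 15 becomes 42,000 ÷ 45,000 = 93.3%. It does not correct a skipped cycle: with Cycle 3 skipped it gives 36,000 ÷ (3000 × 3 × 4) = 100%. If (b) is adopted, say so beside the table. Under either option, state which BSA is used.

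An optional addition, not a correction, is a relative dose intensity over elapsed time: (cumulative mg/m² ÷ elapsed days) ÷ (assigned mg/m²/day × 3 ÷ 21), with elapsed days running from the first chemotherapy dose to the start of the last chemotherapy cycle given plus 21 days. It would show a skipped Cycle 3 as (36,000 ÷ 105) ÷ (9000 ÷ 21) = 80.0%, and one 7-day delay in five full cycles as 105 ÷ 112 = 93.8%.

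No dose or clinical rule changes under any of these.

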5.6.1.2 Study Drug Administration

Total cumulative dose per subject (mg) will be summarized separately for lenvatinib, ifosfamide and etoposide by descriptive statistics. It is calculated as the sum of daily doses.

Dose intensity (mg/m²/day) will be summarized separately for lenvatinib, ifosfamide, and etoposide by descriptive statistics. It is calculated as: Total cumulative dose per subject (mg)/BSA (m²)/ Duration of treatment (day).

The percentage of received dose relative to planned dose will be summarized separately for lenvatinib, ifosfamide and etoposide by descriptive statistics. It is calculated as: dose

intensity / planned dose level $\times 100$. Interpretation: 100 means received dose was the same as the planned, 90 means that the actual dose was 90% of the planned.

5.6.1.3 Study Drug Dose Modifications

Study drug dose modifications will be summarized separately for lenvatinib, ifosfamide, and etoposide, respectively.

Number of subjects with dose reductions, treatment interruptions, and treatment discontinuation due to AEs will be summarized by counts and percentage according to dosing data. Cycle of first dose interruption/reduction, and treatment discontinuation will be summarized by descriptive statistics. Frequency of dose interruptions will also be summarized by appropriate categories (e.g., 1, 2, 3, ≥ 4). Frequency of dose reductions will be summarized by categories (1, 2, 3).

The first dose reduction is defined as the first time the subject's daily dose level was reduced to a non-zero value from its maximum designated BSA-adjusted dose level and did not go back to the maximum designated BSA-adjusted dose level due to a reason other than BSA adjustment or dosing error. For example, 17 mg/m^2 followed by 0 mg/m^2 followed by 14 mg/m^2 . If there is only dose interruption with no reduction in dose, such an event will not be considered as a dose reduction. The second and subsequent dose reductions will be defined accordingly. In addition, time to first dose reduction among subjects with dose reduction will also be summarized.

Dose interruptions will only be determined for lenvatinib. Definition of dose interruption:

1. Only includes the scenario that before and after dose 0 mg/m^2 (interruption period), the dose levels are the same. For example: 17 mg/m^2 followed by 0 mg/m^2 and followed by 17 mg/m^2 ; 14 mg/m^2 followed by 0 mg/m^2 followed by 14 mg/m^2 .
2. If dose level reduces from previous dose level after dose interruption period (dose 0 mg/m^2), it should count as dose reduction and not dose interruption. For example: 17 mg/m^2 followed by 0 mg/m^2 followed by 14 mg/m^2 , the period with 0 mg/m^2 should not count as dose interruption instead it should count as dose reduction.
3. If after dose level 0 mg/m^2 , the subject discontinued from treatment permanently, it should count as treatment discontinuation instead of dose interruption.

Subject data listings will be provided for all dose administration records and for the variables calculated as above.

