9.4.1.2 Lenvatinib Dose Reduction and Interruption Instructions

Dose adjustments will be made for subjects who experience treatment-related toxicity according to the instructions provided in the [Table 3](#). Doses in the Dose Adjustment column are based on a presumed starting dose of 11 mg/m².

Dose reductions occur in succession based on the previous dose level. Each dose level reduction is a 20% reduction from the previous dose. Once the dose has been reduced, it cannot be increased at a later date.

Table 3 Criteria for Temporary Discontinuation of Study Drug, Dose Reduction, and Resumption of Treatment

Lenvatinib Related Toxicity ^{a, b} including hepatic injury and thromboembolic events	Management	Dose Adjustment
Grade 1		
	Continue treatment	No change
Intolerable Grade 2^c or Grade 3^e		
First occurrence	Interrupt until resolved to Grade 0 - 1 or baseline	8.8 mg/m ² (or 20% reduction of the starting dose) orally QD (one-level reduction)
Second occurrence		
(same toxicity or new toxicity)	Interrupt until resolved to Grade 0 - 1 or baseline	7.0 mg/m ² (or 20% reduction of the previous dose) orally QD (one-level reduction)
Third occurrence		
(same toxicity or new toxicity)	Interrupt until resolved to Grade 0 - 1 or baseline	5.6 mg/m ² (or 20% reduction of the previous dose) orally QD (one-level reduction)
Fourth occurrence		
(same toxicity or new toxicity)	Interrupt until resolved to Grade 0 - 1 or baseline	Discuss with sponsor
Grade 4^d: Discontinue Study Treatment		

For grading, see Common Terminology Criteria for Adverse Events (CTCAE v4.03) ([Appendix 2](#)). Collect all CTC grades of adverse events, decreasing and increasing grade.

- a. Interruption of lenvatinib treatment for more than 28 days (due to lenvatinib-related toxicities) will require a discussion with the sponsor before treatment can be resumed.
- b. Initiate optimal medical management for nausea, vomiting, and/or diarrhea before any lenvatinib interruption or dose reduction.
- c. Applicable only to those Grade 2 toxicities judged by the subject and physician to be intolerable. Not applicable to abnormal clinical laboratory values that are not clinically relevant based on the judgment of the investigator.
- d. Excluding laboratory abnormalities judged to be non-life-threatening, in which case manage as Grade 3.

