9.7.1.7 Safety Analyses

All safety analyses will be performed on the Safety Analysis Set. The incidence of treatment-emergent adverse events (TEAEs) and SAEs will be summarized by study cohort, and dose-level, if appropriate. Laboratory test data, vital signs, 12-lead ECGs, urine dipstick, occult blood in stool, Lansky play scores or Karnofsky performance scores, physical examination, height, and closure of proximal tibial plates at scheduled time points and their changes from baseline will be summarized by study cohort and group using descriptive statistics, as appropriate. Abnormal values will be flagged. Prior and concomitant medications, medical/surgical history and subject demographics will be summarized and listed by study cohort and group.

EXTENT OF EXPOSURE

The number of cycles/days on treatment, quantity of study drug administered, and the number of subjects requiring dose reductions, treatment interruption, and treatment discontinuation due to adverse events will be summarized.

ADVERSE EVENTS

The AE verbatim descriptions (investigator terms from the CRF) will be classified into standardized medical terminology using the Medical Dictionary for Regulatory Activities (MedDRA). Adverse events will be coded to the MedDRA (Version 16.1 or higher)

lower level term (LLT) closest to the verbatim term. The linked MedDRA preferred term (PT) and primary system organ class (SOC) will also be captured in the database.

A treatment-emergent adverse event (TEAE) is defined as an AE that emerges during treatment (and within 30 days of the last study treatment), having been absent at pretreatment (Baseline), or

- Reemerges during treatment, having been present at pretreatment (Baseline) but stopped before treatment, or
- Worsens in severity during treatment relative to the pretreatment state, when the AE is continuous.

Only those AEs that are treatment-emergent will be included in summary tables. All AEs, treatment-emergent or otherwise, will be presented in subject data listings.

An overview table, including the incidence of and the number of subjects with treatment-emergent adverse events (TEAEs), SAEs, deaths, and TEAEs that led to discontinuation, dose modification, or dose interruption will be provided.

The TEAEs will be summarized by study cohort and dose level, as appropriate. The incidence of TEAEs will be reported as the number (percentage) of subjects with TEAEs by SOC and PT.

LABORATORY VALUES

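### The dosing-data interruption summary counts only same-dose resumptions, so toxicity holds that follow protocol Table 3 at the first three occurrences never enter it

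*SAP*

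**What the plan says.** **What is to be reported.** Protocol 9.7.1.7 (Extent of Exposure) says the number of subjects "requiring dose reductions, treatment interruption, and treatment discontinuation due to adverse events will be summarized". SAP 5.6.1.3 carries this over: "Number of subjects with dose reductions, treatment interruptions, and treatment discontinuation due to AEs will be summarized by counts and percentage according to dosing data". It adds the frequency of interruptions (1, 2, 3, ≥4) and the cycle of first interruption.

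**How an interruption is defined.** SAP 5.6.1.3 gives three rules, for lenvatinib only.
- Rule 1, in the part that reads "interruption period), the dose levels are the same", limits an interruption to a 0 mg/m² period with the same level on both sides.
- Rule 2 covers a zero period followed by a lower level: "it should count as dose reduction and not dose interruption". Its worked example (17, then 0, then 14 mg/m²) repeats that the zero period "should not count as dose interruption instead it should count as dose reduction".
- Rule 3 covers a zero period followed by a permanent stop: "it should count as treatment discontinuation instead of dose interruption".

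**What the protocol prescribes.** In Protocol 9.4.1.2, Table 3, the management entry at every occurrence of intolerable Grade 2 or Grade 3 lenvatinib-related toxicity is "Interrupt until resolved to Grade 0 - 1 or baseline". The dose-adjustment entry at the first occurrence reads in part "or 20% reduction of the starting dose) orally QD (one-level reduction". The second and third occurrences each bring a further one-level reduction. A reduced dose is not raised again. At the fourth occurrence the resumption dose is left to discussion with the sponsor, and Grade 4 toxicity is a stop. Protocol 9.4.1.4 also pairs interruption with a one-level reduction for persistent, and then recurrent, severe hypertension.

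**The concern.** Table 3 treats the hold and the later reduction as two actions, in two columns. The SAP collapses them into one and keeps only the reduction. A row described as subjects with interruptions due to AEs therefore excludes the holds that the protocol itself prescribes for the first three occurrences of the commonest kind of managed toxicity in Table 3, while any hold resumed at the same level qualifies under the definition.

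What is at stake is tolerability reporting. Protocol 9.2 describes this as the first pediatric study of lenvatinib, and how often the drug had to be withheld is a basic safety description. Protocol 9.7.1.7 contains no same-dose restriction, and SAP Section 7 (Changes in the Planned Analyses) does not list this narrowing. A reader would not learn of it without going to the definition in SAP 5.6.1.3.

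**Working it through.** The plan states no figure to reproduce. The check applies the three SAP rules to the dose sequences that the protocol prescribes.

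**Step 1: does each Table 3 resumption land on a lower level?** Table 3 is printed for a presumed start of 11 mg/m² with 20% steps: 11 × 0.8 = 8.8; 11 × 0.8² = 7.04; 11 × 0.8³ = 5.63. These match the printed 8.8, 7.0 and 5.6. The same holds from the 14 mg/m² recommended dose (14 × 0.8 = 11.2). So occurrences 1 to 3 always fall under Rule 2 when Table 3 is followed.

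**Step 2: classify the sequences under SAP 5.6.1.3** (levels in mg/m²).

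| Sequence | Zero-dose periods | Interruptions | Reductions | Discontinuations |
|---|---|---|---|---|
| One occurrence: 11–0–8.8 | 1 | 0 | 1 | 0 |
| Three occurrences: 11–0–8.8–0–7.0–0–5.6 | 3 | 0 | 3 | 0 |
| Four, fourth resumed at the same level | 4 | 1 | 3 | 0 |
| Four, fourth ends in a permanent stop | 4 | 0 | 3 | 1 |
| Hold ending in a Grade 4 stop: 11–0–stop | 1 | 0 | 0 | 1 |
| Same-dose hold, e.g. for a procedure: 14–0–14 | 1 | 1 | 0 | 0 |

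**Step 3: read off the effect on each planned summary.**
- *Subject count.* A subject whose only AE-related holds are Table 3 occurrences 1 to 3 is absent. A subject who also has a same-dose AE hold remains in the row.
- *Frequency.* Each Table 3 hold at occurrences 1 to 3 removes one from that subject's count, so up to three are lost. In the third line of the table, four holds are shown as one.
- *Cycle of first interruption.* It is missing for a subject with only Table 3 holds. In the third line it is the cycle of the fourth hold, not the first.

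**Step 4: size.** If k of n subjects have only holds that the rules exclude, the subject row is low by 100 × k/n percentage points compared with counting every AE-related hold. The documents give no event rates, so k is unknown and can in principle run from 0 to n. At planned enrolment each such subject is worth 100/12 = 8.3 points in Cohort 2A and 100/30 = 3.3 points in Cohort 2B at its upper size.

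**Step 5: what counting every hold would give.** The three-occurrence subject would show 3 interruptions and 3 reductions, against 0 and 3 now. The four-occurrence subject would show 4 interruptions, against 1 or 0 now.

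**The case against.** The strongest defence is that the SAP uses an explicit, prespecified hierarchy. Each zero-dose period is classed by its outcome, and all three classes appear in the same summary. On that view a Table 3 hold is moved to the reduction row and nothing is lost. Other planned outputs support this:
- SAP 5.6.2 tabulates TEAEs leading to reduction and/or interruption and lists the corresponding AEs.
- Protocol 9.7.1.7 requires an AE overview that names interruption separately from dose modification.
- SAP 5.6.1.3 lists all dosing records.
- In SAP 5.6.1.1 and 5.6.1.2, duration runs from first to last dose, so zero-dose days inside that span lower the dose intensity whatever they are called.

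Nor does Table 3 govern every AE-related hold. A fourth occurrence, a hold for hypertensive risk (Protocol 9.4.1.4), a hold for suspected but unconfirmed PRES (9.4.1.5) and a hold for an AE unrelated to lenvatinib all count if dosing resumes at the same level.

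Most of this stands, and it rules out two stronger readings that a reader might infer. One is that toxicity interruptions disappear from the report; the reduction row, the TEAE tables and the listings show otherwise. The other is that the row omits all, or some stated percentage, of toxicity interruptions; without event rates no share can be given.

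The defence does not rescue the row itself. The tables itemised in SAP 5.6.2 pool reduction with interruption or show reduction alone. If the AE overview does report interruption separately, its count may differ from the dosing-data row with no stated explanation. A deliberate convention also needs a label that tells the reader what is counted, and the planned wording gives none.

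**Conclusion.** The point holds in a limited form. Under SAP 5.6.1.3, a hold that follows Table 3 at occurrences 1 to 3 always scores zero in the dosing-data interruption count, in its frequency categories and in the cycle of first interruption. Those summaries therefore understate the number of subjects requiring interruption due to AEs, as Protocol 9.7.1.7 describes it.

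The per-subject effect is exact: up to three uncounted holds from these occurrences. The cohort-level effect cannot be computed. The conclusion assumes that sites follow Table 3 and that the SAP rules are programmed as written.

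The consequence is confined to descriptive safety reporting. The efficacy endpoints, hypothesis tests, DLT criteria and recommended dose are not defined through this classification. It is still worth correcting, because the count is one the protocol promises and the correction is cheap.

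**What to change.** In SAP 5.6.1.3, count every 0 mg/m² period due to an AE as an interruption, and cross-classify it by what followed: same dose, lower dose or permanent stop. Count reductions and discontinuations separately, so that a subject may appear in more than one row. Derive the frequency categories and the cycle of first interruption from the same count. If the current definition is also kept, label that row as interruption with resumption at the same dose. Record the definition in SAP Section 7.

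The cost is SAP wording and minor reprogramming on dosing records that are already to be listed. Interruption counts will be higher and the rows will no longer be mutually exclusive, so a footnote should say so. No dosing or management rule changes.
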